- k) **Primary Outcome Measures:** PNAC will be the primary outcome measure and will be defined as direct bilirubin ≥ 2 mg/dl developing within one week of the completion of 6 week randomization period in the absence of other known causes (discussed earlier). Total serum bilirubin and direct bilirubin concentration will be measured once weekly as part of the standard of care when on parenteral nutrition. The direct bilirubin is usually measured until the resolution of direct hyperbilirubinemia as part of the standard of care. If parents have consented, we will collect blood that is leftover from blood draws that are done as part of standard of care.

The blood samples will be stored in -80 degree freezer in the PI's laboratory within the Department of Neonatology for possible future research on intravenous nutrition and its effects on the liver such as identifying a more sensitive biochemical marker than direct bilirubin concentration of liver injury. Samples will be stored with a study number only and will only be linked to the data collected for the purposes of this study. Only study team members will have access to the stored blood and will be able to use the samples. Future research on stored blood after completion of this study will only be conducted by the PI on IRB approval.

- l) Secondary Outcome measures:** Secondary outcome measures will include peak direct bilirubin concentrations during hospital stay, use of choleretic medications and use of Omegavan during the hospital stay and percentage weight gain during the 6 week study period.
- m) Data Safety Monitoring:** There are several reasons why independent data safety monitoring and stopping rules were not considered for this study as described below:
 - 1) In this study, the outcome measure, direct hyperbilirubinemia $>2.0\text{mg/dL}$, is the potential side effect of interest secondary to intravenous lipid intake. As per the standard of care, the intravenous lipid intake of 1-2 gm/kg/day is routinely used in the presence of direct hyperbilirubinemia of 2 mg/dL to provide essential calories and prevent essential fatty acid deficiency. Usually, choleretic medications such as cholecystokinin are used to resolve PNAC at this point.

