 - 2) Our hypothesis is that the development of PNAC is causally related to the cumulative lipid intake, however, protein and glucose intake may modify the association between lipid intake and PNAC. In addition, sepsis and prematurity are confounding risk factors. The sample size calculated ($n=40$) to evaluate the outcome measure (or the adverse event) accounts for the variable duration of the TPN (cumulative lipid intake) and presence of confounding risk factors. Therefore, meaningful statistical analysis is not possible with an interim analysis of less than 40 subjects.
 - 3) As suggested by our observational study, a mean cumulative dose of 55gm/kg (SD 15) of intravenous lipid is required before the development of PNAC in late preterm and term

infants. Thus, it is expected that an infant on 1gm/kg/day of intravenous lipid arm will take ~ 55 days to develop PNAC. Therefore, considering the fact that TPN intake will often be less than 42 days among study subjects, not all infants in either group are expected to develop PNAC. PNAC, the study outcome, as defined for the purpose of the study, is the earliest when any medications are used to treat PNAC as per the standard of care. Severe PNAC is defined when direct bilirubin concentration is > 10 mg/dL and is very rare. The randomization of intravenous lipid intake will be stopped long before severe PNAC may be seen among enrolled subjects.

- 4) Performing interim analyses will require more stringent significance level which will increase the sample size required to perform the study. This is a pilot study performed as part of fellow's project for which 40 subjects are required for meaningful analysis of outcome (or adverse event)
- 5) This study has been designed as a block randomization with each block having 8 subjects with 1:1 assignment, so even if all enrolled infants were to develop PNAC, it will suggest that there is no difference between the two groups and there is no causal association between intravenous lipid intake and cholestasis.

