Because of reasons mentioned even if the first 20 subjects (50%) hit the direct bilirubin endpoint, interim analysis is unlikely to allow meaningful analysis of the causation between lipid intake and the outcome measure (or adverse event) as provided in the protocol. In other words, it is unlikely to reach adjusted statistical significance required for interim analyses. Thus, since the outcome measure and the adverse event are the same and the sample size required to evaluate the association (or the adverse event) controlling for other factors is 40, no interim analysis and stopping rules were considered for this pilot study. For trial management, the investigation team will track enrollment and protocol compliance and review every 3 months.

V. DATA COLLECTION: The baseline data on demographics and clinical factors (antenatal and postnatal) before randomization on each subject will be collected. Similarly, data on clinical factors will be collected during the 6 week study period or until the subject is receiving intravenous lipid as per

randomization or until the subject develops PNAC (direct bilirubin ≥ 2 mg/dl in the absence of concurrent infection).

The information on TPN components, specifically amount of lipid, protein, and glucose intake on each day will be prospectively collected using pharmacy and TPN records. Information on cumulative amount of lipid intake, cumulative amount of protein intake, and cumulative amount of glucose intake will be determined for all enrolled subjects. The additional information that will be collected is duration (days) of TPN, use of trace elements, duration (days) of NPO, type of enteral feeds (maternal breast milk vs. Formula) duration (days) of antibiotic use, onset and duration of choleric medications, sepsis defined as blood culture positivity or clinical signs and symptoms of sepsis with the use of antibiotics for > 3 days, day of life when the infant reaches an enteral intake of 120 ml/kg/day, duration (days) of mechanical ventilation, duration of CPAP, duration of oxygen supplementation, and amount of erythrocyte transfusions during the study period. However, use of choleric medications and discontinuation of trace elements from the TPN is not expected during the study period based on the unit policy as delineated earlier.

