VI. SAMPLE SIZE CALCULATION: Assuming a 4-week median follow-up time and an incidence rate of 40% for 6 weeks in control group, a two-sided log rank test with an overall sample size of 40 subjects (20 per group) achieves 80.0% power at a 0.050 significance level to detect a hazard ratio of 3.6.

Power	Incidence Rate	N Control	N Study	Haz Ratio (HR)
0.8	40%	20	20	3.6
0.8	50%	20	20	3.26
0.8	60%	20	20	3.02

Kaplan-Meier (KM) estimates of survival function will be provided and compared between groups. Log-rank test will also be used to compare time to endpoint. Cox proportional hazards model will be fitted after controlling for covariates which are found to be imbalanced in preliminary analysis. Estimate of hazard ratio and associated confidence interval will be obtained.

VII. DATA ANALYSES AND MONITORING:

a) **Randomization:** Upon successful completion of necessary screening assessments and being confirmed to be eligible by the investigator, subjects will be randomized in 1:1 ratio to two groups: 1) 1 g/kg/day intravenous lipid and 2) 2 g/kg/day intravenous lipid. Each subject will be assigned a unique sequential subject number for identification throughout the entire course of the study. The subject number will not be reused for any other participant in the study. Subjects who are discontinued or withdrawn from the study prior to randomization will be replaced. In addition, subjects who are identified to have direct hyperbilirubinemia from causes other than parenteral nutrition or did not require parenteral nutrition for more than 2 weeks will be considered screen failure and will also be replaced. We anticipate a total number of 52 subjects to participate in the study to complete the study on 40 subjects. During the study, the treatment assignments will be available only to the RP.

c) **Samples for Analysis:** The “Intent-to-Treat” sample includes all subjects who are randomized into the study. Subjects will be grouped according to the treatment to which they are randomized.

d) Statistical Analyses:

General statistical Considerations:

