All statistical analyses will be conducted using Version 10 of the SAS System for Windows (Copyright © 2002-2003 SAS Institute Inc., Cary, NC, USA.) by a biostatistician. Descriptive statistics will be used to summarize outcomes by treatment groups. For continuous variables, descriptive statistics will include the mean, median, standard deviation, minimum, maximum, number of available observations, and number of missing observations. For discrete variables, descriptive statistics will include frequencies and percentages, number of available observations and numbers of missing observations.

We will determine whether there are important baseline differences between the two groups despite randomization with respect to participant characteristics (e.g., gender, race/ethnicity, GA at birth, SGA[<10th percentile]). If any important differences are found, the primary analyses will be repeated after statistically adjusting for these differences. If distributional assumptions associated with a particular statistical procedure are violated, appropriate transformations will be made or non-parametric alternatives will be used (e.g., Wilcoxon rank sum tests in place of two-sample t-tests). Infants enrolled but subsequently found to meet exclusion criteria will be analyzed separately.

The incidence rate of PNAC will be compared between the 2 groups using Kaplan Meier curves. Subjects who reach full enteral feeds before 6 weeks of study period will be censored. Kaplan-Meier (KM) estimates of survival function will be provided and compared between groups. Log-rank test will also be used to compare time to endpoint. Cox proportional hazards model will be fitted after controlling for covariates which are found to be imbalanced in preliminary analysis. Estimate of hazard ratio and associated confidence interval will be obtained.

The potential confounders are sepsis, use of choleric medications and trace elements. Incidence of nosocomial sepsis has decreased remarkably over the last few years in our unit and with

randomization we do not anticipate significant group differences in the incidence of sepsis. The use of choleric medications and discontinuation of trace elements should occur after the development of primary outcome as per the unit policy and therefore these factors are unlikely to confound the relationship between the lipid intake and PNAC.

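### No direct bilirubin is required when parenteral nutrition stops, so an infant can be censored with up to 7 days of lipid exposure never assessed for the primary endpoint

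*Combined protocol and SAP*

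**What the plan says.** Section IV(k) gives the schedule: "Total serum bilirubin and direct bilirubin concentration will be measured once weekly as part of the standard of care when on parenteral nutrition". It then adds: "The direct bilirubin is usually measured until the resolution of direct hyperbilirubinemia as part of the standard of care". That second sentence helps only infants whose value has already been found raised.

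The same section defines the endpoint as "direct bilirubin ≥ 2 mg/dl developing within one week of the completion of 6 week randomization period", so the extra week is attached to the end of the 6-week period and not to an earlier PN stop.

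Section VII(d) states: "Subjects who reach full enteral feeds before 6 weeks of study period will be censored". It gives no censoring date. Section V lets collection of clinical data end when the randomized lipid ends.

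On PN duration, section IV(m), reason 3, expects that "TPN intake will often be less than 42 days among study subjects". Section VII(a) replaces infants who "did not require parenteral nutrition for more than 2 weeks will be considered screen failure". The exits of interest therefore fall mainly between about day 14 and day 42.

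**The concern.** The endpoint can be seen only when blood is drawn. With weekly draws that stop with PN, an infant whose last value was below 2 mg/dl and who comes off PN before the next draw has no scheduled value for the intervening days. Section IV(k) schedules no later one. If direct bilirubin crossed 2 mg/dl in those days, the infant enters the analysis as event-free.

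This matters here for two reasons. The hypothesis concerns cumulative lipid, so the unassessed days are those with the highest cumulative dose. And the trial is sized at 80% power with about 20 expected events, so a loss of one or two events is visible.

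**Working it through.** **Inputs from the plan.** Draws every 7 days on PN (IV(k)). 20 infants per group, two-sided 0.05, 80% power, 40% control incidence at 6 weeks, hazard ratio 3.6, 4-week median follow-up (VI). Mean cumulative lipid at onset 55 g/kg, SD 15 (IV(m), reason 3).

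**Assumptions.** The gap between last draw and PN stop is uniform on 0 to 7 days. PN stops at day 28 for all, or uniformly over days 14 to 42. Section VI does not name its control arm; I take it as 1 g/kg. The initial step from 1 to 2 g/kg is ignored.

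**1. The plan's power.** Constant control hazard: h = −ln(0.60)/42 = 0.01216 per day. Expected events by day 28:
- control: 20 × (1 − e^(−28h)) = 20 × (1 − 0.711) = 5.77
- hazard ratio 3.6: 20 × (1 − e^(−3.6×28h)) = 20 × (1 − 0.293) = 14.13

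The total is 19.90. Schoenfeld power = Φ(√19.90/2 × ln 3.6 − 1.96) = 0.815, which agrees with the stated 80% to within 2 points.

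**2. Size of the gap.** The mean is 3.5 days: 3.5 g/kg of lipid in the 1 g/kg arm and 7 g/kg in the 2 g/kg arm.

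**3. Missed events, section VI hazards, PN stop at day 28.** Averaging over the gap, missed events per arm = 20 × S(28) × [(e^x − 1)/x − 1], where x = 7 × hazard and S(28) is the event-free proportion.
- control: x = 0.0851; 20 × 0.711 × 0.0438 = 0.62
- hazard ratio 3.6: x = 0.3065; 20 × 0.293 × 0.1702 = 1.00

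The total is 1.62 of 19.90. With PN stops over days 14 to 42, simulated losses are 3.1 and 5.4 percentage points, or 20 × (0.031 + 0.054) = 1.7 events.

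**4. Power.** With 19.90 − 1.62 = 18.28 events, Schoenfeld power is 0.782, against 0.815. Simulated log-rank power with PN stops over days 14 to 42 (1,500 trials) is 0.765 with continuous observation, 0.724 with weekly draws only, and 0.752 with a draw at PN stop. Over four assumed PN distributions it is 0.68 to 0.80 with weekly draws only and 0.72 to 0.83 with a stop draw.

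**5. Threshold model.** Onset occurs when cumulative lipid passes a normal threshold, 55 (SD 15) g/kg.
- PN stop at day 28: 0.28 + 3.54 = 3.82 missed events (up to about 3.9 in simulation)
- PN stops over days 14 to 42: 0.38 + 2.29 = 2.67

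The power loss is roughly 5 to 11 points; for PN stops over days 14 to 42, power falls from 0.984 to 0.931.

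**6. Split between arms.** Share of missed events in the 2 g/kg arm:

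| Model | PN stop day 28 | PN stop day 42 |
|---|---|---|
| 40%, HR 3.6 | 62% | 51% |
| 50%, HR 3.26 | 56% | 43% |
| 60%, HR 3.02 | 49% | 35% |
| Threshold 55 (SD 15) | 93% | 48% |

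If lipid has no effect, the share is 50%.

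**7. Effect on the contrast.** In step 3 the control arm loses 0.62/5.77 = 11% of its events and the other arm 1.00/14.13 = 7%. The ratio of event counts goes from 14.13/5.77 = 2.45 to 13.13/5.15 = 2.55. The absolute difference falls from 8.36/20 = 41.8 points to 7.98/20 = 39.9 points. For PN stops over days 14 to 42, the simulated event-rate ratio is 3.54 with continuous observation, 3.33 with weekly draws and 3.22 with a stop draw added, so the missing stop value is not what pulls the ratio down. With no effect, simulated type I error under weekly draws is 0.04.

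**The case against.** The strongest reply is that the loss is small: in the base planning case under two events and about 4 points of power, in a self-described pilot. Routine draws after PN are not forbidden, and the secondary outcome of peak direct bilirubin over the hospital stay suggests that some later values will exist. That stands; the actual loss could be smaller than calculated. It is not secured, however, because nothing requires such a value or says that it counts.

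The larger figures also rest on a model that sits poorly with section VI. The 55 (SD 15) g/kg threshold implies 19% incidence at day 42 in the 1 g/kg arm, against 40% in control if that arm is the control. It also assumes full dosing throughout. It is best read as an upper case.

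Three stronger readings are tempting, and the documents do not support them:
- **Most missed events fall in the 2 g/kg arm, biasing the trial against an effect.** The split depends on the model and ties or reverses in section VI's other rows. The absolute incidence difference shrinks somewhat, but the planned analysis is a log-rank test and a Cox hazard ratio, and step 7 shows no dilution from this gap.
- **The plan credits unmeasured days as event-free up to the date of full feeds.** Section VII(d) says that these infants are censored, but not on what date.
- **Most infants leave PN before 42 days.** Section IV(m) says this will be so often; it gives no proportion.

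**Conclusion.** The gap is real as written. An infant who stops PN before 6 weeks can be censored with up to 7 days of exposure, at the highest cumulative dose, never assessed. Under section VI's 40% and hazard ratio 3.6 this costs about 1.6 to 1.7 of roughly 20 expected events and about 4 points of log-rank power. Under the threshold model it costs about 2.7 to 3.9 events. Both ranges rest on the assumed PN-stop times, a uniform draw phase and no unscheduled later values.

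The consequence is lost events, lower power and understated incidence in both arms. It is not a demonstrated bias in the hazard ratio or a threat to type I error. It merits a change because the remedy is cheap, not because the trial is invalid without it.

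**What to change.** In IV(k), keep the weekly schedule and add one direct bilirubin at PN stop, or on the first routine sample within the following 7 days. Count a value of 2 mg/dl or more there, absent other known causes, as a primary event. This gives infants who stop early an assessment comparable to the one-week window already allowed after week 6.

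In VII(d), state that infants without an event are censored at that final assessment.

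The two changes belong together. Moving the censoring date back to the last value below 2 mg/dl without adding the stop value recovers no events and slightly lowers simulated power (0.72 to 0.71 under section VI's hazards, 0.93 to 0.89 under the threshold model). Adding a value is also preferable to re-timing a weekly draw, which needs the stop date in advance and can stretch the preceding interval beyond 7 days.

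The cost is one laboratory value per infant, from a sample already taken for care where possible, and two sentences of text. In the base case it recovers most or all of the lost power.

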**EFFECT OF LIPID INTAKE ON DIRECT HYPERBILIRUBINEMIA IN LATE PRETERM
AND TERM INFANTS WITH GASTROINTESTINAL SURGICAL PROBLEMS**

NCT01555957

I. PURPOSE OF THE STUDY AND BACKGROUND

The purpose of the study is to establish a cause and effect relationship between lipid intake and the incidence of direct hyperbilirubinemia (cholestasis) in late preterm and term infants with major gastro-intestinal (GI) surgical disorders such as gastroschisis, omphalocele, volvulus, TE fistula, duodenal atresia, jejunal atresia, ileal atresia, Hirschsprung's disease, anorectal malformation, intestinal obstruction and GI perforations requiring surgery. Infants with major GI surgical disorders as mentioned above will be randomized to receive 1gm/kg/day or 2gm/kg/day of 20% intralipids within the first 72 hours after birth. The study is not open to all surgical infants because infants with other surgical problems can be fed enterally within few days after surgery and usually do not require TPN for prolong periods (>2 weeks). Also infants with major GI surgical disorders have similar clinical course, undergo similar type of operative procedures, and have similar complications thus eliminating potential confounding factors. The primary outcome measure is the incidence rate of parenteral nutrition associated cholestasis (PNAC). PNAC will be defined as serum direct bilirubin $\geq 2\text{mg/dl}$ in the absence of other known causes of direct hyperbilirubinemia as described under exclusion criteria.

II. BACKGROUND AND JUSTIFICATION:

Since its introduction in the late 1960s, total parenteral nutrition (TPN) has established itself as an effective mode for parenteral hyperalimentation in patients with acute or chronic intestinal failure. Out of the many complications of parenteral nutrition, the most common is the cholestasis often referred to as Parenteral Nutrition Associated Cholestasis (PNAC). PNAC is defined clinically using

direct bilirubin as an index measure in the absence of other known causes of direct hyperbilirubinemia (see exclusion criteria). The reported incidence of PNAC in neonates is as high as 84%. [1, 2]

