PNAC was first described by Peden and colleagues [3] and has long been recognized as a major cause of morbidity and mortality in neonates and infants. [4, 5] PNAC can be associated with liver dysfunction, cirrhosis, and hepatic carcinoma. The proposed mechanisms that could explain cholestasis caused by the total parenteral nutrition are multifactorial. The major mechanisms include hemodynamic modifications within the biliary system caused by parenteral administration of nutrients, bile stasis resulting from decreased stimulation of gastrointestinal hormones in the absence of any enteral intake, direct toxic effects of TPN components, premature biliary system, and bacterial overgrowth leading to overproduction of deconjugated bile acids. Very few observational studies done earlier have looked at the association of PNAC with various nutritional components of TPN. The findings of these studies indicate that PNAC could be associated with increased duration of TPN [6, 7] with almost all infants developing PNAC by 6 weeks on TPN [8,9,10], higher intake of amino acids [11], higher intake of dextrose, intake of trace elements like aluminium [12], copper and manganese [13], and cumulative amount of intravenous lipid intake[14]. Several preventive trials have been conducted in neonates involving the use of different amounts of protein intake or the use of choleretic medications in order to prevent cholestasis. Vileisis and colleagues [11] did not find any difference in the incidence of PNAC when they compared amino acids intake of 2.3gm/kg/day vs. 3.6 gm/kg/day. Their findings were reciprocated by Clark and colleagues [15] who found no difference in the incidence of PNAC when comparing amino acids supplementation of 2.5 vs. 3.5gm/kg/day. Similarly, the use of both cholecystokinin (CCK) [16], and ursodeoxycholic acid [17] failed to prevent the development of PNAC. Majority of these preventive trials performed in neonates defined PNAC as direct bilirubin ≥ 2 mg/dL after two weeks on PN [9, 11, 21]. Because these preventive trials failed to identify any

preventive therapy, there is a need to identify alternative ways to prevent PNAC in high-risk infants.

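### Does the claim in section IV.m that universal PNAC would show no difference between arms undermine the planned time-to-event analysis?

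*Combined protocol and SAP*

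**What the plan says.** Section IV.m lists five reasons for having no independent monitoring and no stopping rules.

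- Reason 2: "meaningful statistical analysis is not possible with an interim analysis of less than 40 subjects". The ground given is variable TPN duration and confounding risk factors.
- Reason 3: PNAC needs a mean cumulative lipid dose of 55 g/kg (SD 15), about 55 days at 1 g/kg/day. TPN will often last less than 42 days, so "not all infants in either group are expected to develop PNAC".
- Reason 4: "Performing interim analyses will require more stringent significance level which will increase the sample size required to perform the study".
- Reason 5 starts from 1:1 blocks of eight and says that "even if all enrolled infants were to develop PNAC, it will suggest that there is no difference between the two groups" and that no causal association exists.
- Closing paragraph: "even if the first 20 subjects (50%) hit the direct bilirubin endpoint, interim analysis is unlikely to allow meaningful analysis of the causation", and adjusted significance is unlikely.

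The analysis is set out elsewhere. Section VI says that 20 infants per group "achieves 80.0% power at a 0.050 significance level to detect a hazard ratio of 3.6" with a two-sided log-rank test. Sections VI and VII.d specify Kaplan-Meier curves, the log-rank test, a Cox model, and a hazard ratio with confidence interval. Infants who reach full enteral feeds before 6 weeks are censored.

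**The concern.** Reason 5 treats the outcome as a crude proportion, while the plan compares times. If every infant developed PNAC but the 2 g/kg/day arm did so much sooner, the log-rank test could show a clear effect that reason 5 would call no effect. Reason 3 itself argues from timing: 55 g/kg takes about 55 days at 1 g/kg/day and, by the same arithmetic, 55/2 = 27.5 days at 2 g/kg/day. Nor is universal PNAC foreign to section II, which reports "almost all infants developing PNAC by 6 weeks on TPN" and says "The reported incidence of PNAC in neonates is as high as 84" per cent.

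Two further points looked wrong. Log-rank information accrues with events, yet IV.m counts infants. And the sample-size cost of one interim look can be very small. The section justifies having no monitoring in a trial whose outcome is also its adverse event, so a false argument there could mislead readers or shape the final conclusion.

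**Working it through.** **Inputs.** Section VI: 20 per arm; control incidence 40%, 50% or 60% by 6 weeks with HR 3.6, 3.26 or 3.02; two-sided 0.05; 4-week median follow-up. Section IV.k: outcome window of 6 weeks plus one, so 7 weeks. Section IV.m: 55 (SD 15) g/kg. Section II: 84%, given without a time frame. Assumptions: exponential event times (except under the dose model), and the 1 g/kg/day arm is the control.

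**1. The stated power.** Control hazard λ = −ln(1−p)/6 per week. Expected events d = 20[(1−e^(−λT)) + (1−e^(−λ·HR·T))].

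| Control, HR | d at T=4 | Schoenfeld power, Φ(√(d/4)·ln HR − 1.96) | d at T=6 | Freedman power, Φ(√d·(HR−1)/(HR+1) − 1.96) |
|---|---|---|---|---|
| 40%, 3.6 | 19.9 | 81.5% | 24.8 | 80.4% |
| 50%, 3.26 | 23.0 | 80.8% | 27.9 | 80.0% |
| 60%, 3.02 | 26.0 | 80.4% | 30.7 | 79.6% |

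Both readings reproduce the stated 80%, so the documents do not settle whether the base case assumes about 20 or about 25 events.

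**2. Does universal PNAC imply no difference?** Simulated trials (20 v 20) were conditioned on every infant having PNAC inside the window. The share with log-rank p<0.05 was:

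- Section VI hazards, 7 weeks: 26%, 32–33% and 40–41% for the three rows.
- Control incidence 84% by 7 or by 6 weeks, with HR kept at 3.6: about 86% and 90%.
- Reason 3's dose model: about 99.5% with a 7-week window and 87% with a 6-week window.

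So "no difference" does not follow in any case, although at the design's own hazards a non-significant result is the likelier one.

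**3. How likely is the scenario?** P(all 40 by 7 weeks) = [(1−e^(−7λ))(1−e^(−7λ·HR))]^20.

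- 40% row: (0.449 × 0.883)^20 = 9×10⁻⁹.
- 50% row: (0.555 × 0.928)^20 = 2×10⁻⁶.
- 60% row: (0.657 × 0.960)^20 = 1×10⁻⁴.
- Dose model: Φ((49−55)/15) = 0.345 and Φ((98−55)/15) = 0.998, so (0.345 × 0.998)^20 = 5×10⁻¹⁰.
- Control 84% by 7 weeks, HR 3.6: [0.84 × (1−0.16^3.6)]^20 = 0.03. Read as 84% by 6 weeks: [(1−0.16^(7/6))(1−0.16^(7×3.6/6))]^20 = 0.08.

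These figures ignore censoring at full feeds, which lowers them all.

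**4. Is "50%" wrong?** It is 20/40 infants. As a share of information, 20 events must be set against what the trial would finally have. N is fixed, so 20 more infants follow. At design hazards they add half of 19.9 to half of 30.7 events, about 10 to 15. The fraction is 20/30 = 67% down to 20/35.4 = 57%. If they behave like the first 20, it is 20/40 = 50%. Dividing 20 by the design total alone (65–100%) leaves out the infants still to come.

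**5. Reason 4.** One look at half information multiplies sample size by 1.008 (O'Brien-Fleming), 1.001 (Haybittle-Peto at p<0.001) or 1.11 (Pocock). On 40 infants that is 40.3, 40.0 or 44.4. Every factor exceeds 1.

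**6. The closing sentence.** If the first 20 infants (10 v 10) all have PNAC within 7 weeks at section VI's hazards, the log-rank statistic crosses a Pocock bound (2.178) in 12–19% of simulated trials and an O'Brien-Fleming bound (2.797) in 4–7%. With no limit on event times and HR 3.6 the figures are 65% and 36%, but the plan's window does not allow that. "Unlikely" is fair on the plan's own assumptions.

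**The case for a change.** The strongest case for a change is that reason 5 is false under the plan's own analysis, comes close to a ready-made interpretation, and costs nothing to delete. Reading the outcome as a crude proportion does not rescue it, because section VII.d compares even the incidence rate by Kaplan-Meier curves. If control incidence were as high as section II's 84%, the planned test would detect HR 3.6 in 86–90% of the trials that reason 5 would call negative.

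The logical error stands. Its consequence does not. The 86–90% keeps HR 3.6 at an incidence where section VI's own pattern points lower (HR falls from 3.6 to 3.02 as incidence rises). Extending either method in step 1 to 84% gives a detectable HR of about 2.6–2.7, and at 2.7 the conditional power is 59% (56% with weekly sampling). Section II's six-week statement concerns infants still on TPN at six weeks, while IV.m expects TPN often to end sooner. No analysis section refers to reason 5, so a statistician following sections VI and VII.d would report the log-rank test and hazard ratio whatever share of infants had events.

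On reason 2, an event count would be the better unit for a log-rank test, but the text argues from confounders and TPN duration and makes no claim about information fractions.

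**Conclusion.** Reason 5 is a faulty inference in a supporting argument, and no change to the plan is needed. Universal PNAC would not by itself show the absence of an effect, but the scenario has probability of about 10⁻⁸ to 10⁻⁴ at section VI's hazards and 5×10⁻¹⁰ under reason 3's model. The analysis sections already fix how the conclusion is drawn. The percentage of infants in the closing paragraph is correct as written, reason 4 is true though small for some boundaries, and the doubt about adjusted significance holds at the design hazards. The decision against interim analysis has other stated support: doses in routine use, randomised lipid ending at the endpoint, severe PNAC described as very rare, and pilot size.

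This rests on exponential event times, a 7-week window and interim boundaries chosen for illustration, since the documents name none. At 84% control incidence the scenario is less remote (3–8% before censoring), but sections VI and VII.d would still govern the conclusion. Dropping the sentence is optional tidying.
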